**Temozolomide Dose Reduction Table**

Dose Level	TMZ Dose $\text{mg}/\text{m}^2$
starting dose	150
first dose reduction	100
second dose reduction	off treatment

- If any non-hematological toxicity observed was CTCAE **Grade 4** (except for alopecia, nausea and vomiting) then adjuvant temozolomide treatment should be **stopped** (patient is off treatment).

**Subsequent 5-day TMZ treatments:** Any dose reductions of temozolomide will be determined according to (1) non-hematological toxicity during the preceding treatment cycle, as well as (2) the worst ANC and platelets toxicity. No dose escalation should be attempted. The same dose reductions as for the second 5-day TMZ treatment should be applied.

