**AND**
- 2) All toxicities recovered to  $\leq$  grade 1 [or tolerable grade 2 for non-hematologic toxicity] or  $\leq$  baseline.

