## **5.0 DOSING DELAYS/DOSE MODIFICATION FOR TOXICITY**

Clinically significant adverse events or abnormal laboratory values assessed as unrelated to disease progression, intercurrent illness, or concomitant medications require dose delay and dose modification. Such toxicities must have an attribution of possible, probable, or definite to TRC102 or temozolomide (see Section [9.2.2](#)).

In general, if toxicity occurs that is attributed to only one of the agents, only that agent should be dose-reduced/modified. The dose of the other agent can be maintained at the same level. If multiple toxicities occur, dose modification decisions should be based on the most severe toxicity.

**Because the protocol is designed to look at the effects of a combination treatment of TRC102 with TMZ, if either TRC102 or TMZ is permanently discontinued, the patient will be off treatment.**

For patients experiencing toxicity meeting the criteria below, the attributed drug(s) will be stopped. If the patient recovers ( $\leq$  grade 1 [or tolerable grade 2 for non-hematologic toxicity] or  $\leq$  baseline) a dose reduction is required for subsequent doses. Skipped doses will not be made up. If there is any question or confusion concerning a toxicity, the treating site should contact the ABTC Central Office to determine patient's toxicity status. The ABTC Central Office, with the Study Chair, will make the final decision.

- Hematological toxicities will require dose modification if any of the following occur and complete blood counts and differentials were obtained according to the mandated schedule (CBC, differential, and platelets drawn twice a week until the ANC  $\geq 1500/\text{mm}^3$  and platelets  $\geq 100,000/\text{mm}^3$ ): grade 3 or 4 lymphopenia will not be considered a toxicity requiring dose modification.

- ANC of  $< 500/\text{mm}^3$ .

- Platelets < 25,000/mm^3.
- Febrile neutropenia
- Any hematological toxicity that prevents administration of > 80% of the planned TRC102 and temozolomide doses

➤ Non-hematological toxicities will require dose modification if any of the following occur:

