## 9.0 MONITORING OF PATIENTS

### 9.1 Table of Required Observations

#### Arms 1 & 2 (28-Day Cycles)

	Baseline	Days 1-5 of every cycle	Weekly During Cycle 1	Weekly During All Cycles	Pre-Odd Cycles (cycles 3+)	Pre- Even Cycles	Off Treatment	30 Days post-last dose
TRC102		6						
Temozolomide		7						
Glucocorticoids Dose Evaluation	1				5		8	
AE Evaluation	1		12		5	5	8,10	11
MRI	1				5		8	
H&P/Neuro Exam	1				5	5	8	
KPS	1				5	5	8	
Vital Signs	1,2		12		2,5	2,5	2,8	
CBC, Diff, Platelets	1			9,12	5,9	5,9	8,9	
Serum Chemistry	1,3		12		3,5	3,5	3,8	
APTT or PTT	1							
Serum Pregnancy Test	1,4							
Archived Tumor Tissue	13							

- 1– All baseline measurements must be done within minus 21 calendar days of treatment administration unless otherwise specified.
- 2– Including blood pressure, respiratory rate, heart rate, temperature, weight, height: height is required at baseline only; weight is required at pre-odd cycle evaluations only.
- 3– Including albumin, alkaline phosphatase, total bilirubin, calcium, creatinine, magnesium, phosphorus, potassium, SGOT, SGPT, sodium.
- 4– For women of child-bearing potential.
- 5– Within minus 5 calendar days of cycle start.
- 6– TRC102 is administered orally on Days 1-5 of each 28-day cycle (see Section [4.3.1](#)). Patients are required to keep a medication diary.
- 7– Temozolomide is administered orally on Days 1-5 of each 28-day cycle (see Section [4.3.2](#)). Patients are required to keep a medication diary.
- 8– Evaluations done within +7 days of off treatment date unless indicated: do not repeat: if MRI within minus 14 days of off-treatment date; if H&P/neuro, KPS, labs within minus 5 days of off-treatment date.
- 9– If ANC < 1500 or plts < 100,000, CBCs/differentials will be repeated twice a week until counts are recovered (ANC  $\geq$ 1500 or plts  $\geq$ 100,000) per protocol. If counts are recovered (ANC  $\geq$ 1500 or plts  $\geq$ 100,000) on day of scheduled drawing do not repeat until next protocol schedule day
- 10 – Adverse Events must be followed for at least 30 days from last dose of TRC102.
- 11– Perform within +14 days of the 30-day post-last dose date.
- 12–  $\pm$  1 day
- 13– Unstained slides from initial resection at diagnosis of glioblastoma, if available (see Section [9.5.1](#))

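### Footnote 9 of Section 9.1 lets twice-weekly counts end with one count still low, and Sections 5.0 and 5.2 give incompatible temozolomide rules after grade 4 non-hematologic toxicity

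*Combined protocol and SAP*

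**What the plan says.** **Blood counts.** Footnote 9 of the Section 9.1 table applies when ANC is below 1500 *or* platelets are below 100,000. It says "CBCs/differentials will be repeated twice a week until counts are recovered", and the parenthesis that follows defines recovery as ANC at least 1500 *or* platelets at least 100,000. The next sentence repeats that definition: if counts have recovered "on day of scheduled drawing do not repeat until next protocol schedule day". Section 5.0 describes the same schedule differently. It refers to "complete blood counts and differentials were obtained according to the mandated schedule (CBC, differential, and platelets drawn twice a week until the ANC" is at least 1500 *and* platelets are at least 100,000.

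**Grade 4 non-hematologic toxicity.** Section 5.0 covers toxicity attributed to either drug and treats grades 3 and 4 together, apart from listed exceptions. The attributed drug is stopped and, if the patient recovers, "a dose reduction is required for subsequent doses". Section 5.2 covers temozolomide alone. It reduces by one level for toxicity above grade 2, but the line under its dose table says that for grade 4 ("except for alopecia, nausea and vomiting) then adjuvant temozolomide treatment should be" stopped) the patient comes off treatment.

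**Count triggers.** Section 5.0 requires modification at ANC below 500 or at "Platelets < 25,000/mm 3". Section 5.2 reduces temozolomide at ANC below 1000 or platelets below 50,000. Section 4.3.2 refers to 5.2 for dose reduction in two places: the first-cycle rule and the general rule on delays.

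**The concern.** The Section 9.1 table is where site staff look up when to draw blood. If its footnote is followed as written, any patient with only one low count can drop back to weekly draws while still cytopenic. Section 5.2 sets later temozolomide doses partly by "2) the worst ANC and platelets toxicity", so a lowest count that falls between weekly draws would go unseen. Section 5.0 also ties hematologic dose modification to counts drawn on its own twice-weekly schedule.

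The grade 4 texts matter more for the individual patient. Under one section the patient continues at a lower dose. Under the other, all protocol therapy ends, because permanent discontinuation of either drug takes the patient off both. This is a multicenter study, so sites reading different sections could manage the same event differently. Toxicity is a secondary objective.

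**Working it through.** The plan states no figure on this point, so the check sets the rules side by side and applies them as written.

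**1. Footnote 9 against Section 5.0**

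| ANC | Platelets | Footnote 9 trigger (*or*) | Footnote 9 recovered (*or*) | Section 5.0 recovered (*and*) |
|---|---|---|---|---|
| 900 | 60,000 | yes | no | no |
| 900 | 120,000 | yes | yes | no |
| 1600 | 60,000 | yes | yes | no |
| 1600 | 120,000 | no | yes | yes |

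The middle two rows show the fault. With one low count, the footnote starts and ends the extra monitoring on the same result. It works as intended only when both counts are low, and then only until one of them recovers.

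**2. Size of the monitoring gap.** Weekly counts carry a window of ±1 day (footnote 12), so consecutive draws are 7 ± 2 = 5 to 9 days apart. Twice-weekly draws are 3 to 4 days apart. Over the longest permitted toxicity hold of 21 days, weekly draws give 21/7 = 3 and twice-weekly draws give 2 × 3 = 6.

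**3. Re-dosing.** Sections 4.2, 4.3.2 and 5.2 all require ANC at least 1500 and platelets at least 100,000 before a cycle. Section 4.2 adds "All toxicities recovered to" grade 1 or lower, tolerable grade 2 if non-hematologic, or baseline. The footnote changes none of this.

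**4. Grade 4 non-hematologic toxicity.** Take an event at least possibly due to temozolomide, exempt under neither section, that recovers within 21 days.

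| Current temozolomide dose | Section 5.0 | Section 5.2 |
|---|---|---|
| 150 mg/m2 | resume reduced; the 5.2 table gives 100 mg/m2 | off treatment |
| 100 mg/m2 | next reduction is off treatment | off treatment |

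The sections collide only at the starting dose. There the choice is a reduction of (150 − 100)/150 = 33.3% or the end of both drugs. No action satisfies both texts.

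**5. Count thresholds.** The 5.2 triggers are twice those of 5.0 (1000/500 = 2; 50,000/25,000 = 2). With ANC 700 and platelets 60,000, the 5.0 count triggers are not met and 5.2 requires a reduction. Section 5.0 says when modification is required. It does not say that modification is required only then. Applying the 5.2 reduction therefore complies with both sections.

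**The case against.** The best defense is that the intent is clear. Footnote 9 speaks of counts in the plural and refers to the protocol, and Section 5.0 calls its own rule the mandated schedule, so a sensible site would wait for both counts. The literal reading makes the footnote pointless for a single low count, which suggests a drafting slip. That is probably right about intent, but the slip appears twice in the table that sites use.

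On grade 4, the layout (5.0 general, 5.1 TRC102, 5.2 temozolomide) favors the drug-specific section. The reduced dose of 100 mg/m2 appears only in the 5.2 table, directly above the stop rule, so a site looking up the dose is likely to see that rule. The Central Office and Study Chair also settle doubtful cases. All of this lowers the chance of divergence. None of it says that 5.2 prevails, and Section 5.0 expressly includes temozolomide.

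A reader might also infer that the two sets of count thresholds contradict each other. The documents do not support that: the 5.0 triggers are sufficient conditions, and 4.3.2 points to 5.2 both in cycle 1 and in its general delay rule.

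Nor do the exception lists clearly conflict. Section 5.0 exempts more events than 5.2, including a first DVT or PE and grade 3 hyperglycemia. Whether those exemptions reach temozolomide depends on whether clinically significant toxicity in 5.2 carries the 5.0 definition. Section 5.1 says expressly that it does for TRC102; 5.2 does not say. If it did, the 5.2 triggers at ANC 500–999 and platelets 25,000–49,999 would do little, which favors reading 5.2 on its own terms. The question is open and worth a clause.

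**Conclusion.** Two faults stand. Footnote 9 contradicts Section 5.0 on when twice-weekly counts may end, and Sections 5.0 and 5.2 cannot both be followed after a non-exempt grade 4 non-hematologic toxicity attributed to temozolomide in a patient at 150 mg/m2.

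The severity is minor. The footnote thins monitoring during cytopenia to about 3 rather than 6 draws in a 21-day hold. This assumes that a site follows the footnote over Section 5.0 and that weekly draws continue through the hold. A reader might infer that patients could be re-dosed with a low count; the cycle-start rules rule that out. The documents give no event rates, so the number of patients affected cannot be stated. Response boundaries, alpha and power are unaffected. The absence of a DLT definition for the Arm 2 safety run is a separate omission and adds no weight here.

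**What to change.** 1. In footnote 9 of Section 9.1, change *or* to *and* in both recovery definitions (ANC at least 1500 and platelets at least 100,000). Keep *or* in the trigger.
2. Add to Section 5.0 a statement that Section 5.2 governs temozolomide dose modification, including its triggers of ANC below 1000 or platelets below 50,000 and off treatment at grade 4 non-hematologic toxicity, while Sections 5.0 and 5.1 govern TRC102. Say in the same place whether the 5.0 exceptions apply to temozolomide.

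The cost is protocol wording only, with no added patients. Compared with Section 5.0, no blood draws are added. Compared with footnote 9 read literally, there are about 6 − 3 = 3 more in a 21-day hold.

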### 5.3 Major Events

Major Events are non-treatment-related grade 3 and 4 hematologic and non-hematologic toxicities. Treatment should be delayed for major events if TRC102 may further complicate the non-treatment-related event. If a major event requires a delay of treatment, treatment must be delayed until toxicity is resolved ( $\leq$  grade 1 [or tolerable grade 2 for non-hematologic toxicity] or  $\leq$  baseline). If toxicity is not resolved in  $\leq 28$  days, the

patient will be removed from treatment. The ABTC Central Office should be consulted if you are not clear on whether to continue or delay treatment.

#### **5.4 Use of Hematologic Growth Factors**

No growth factors (G-CSF or GM-CSF) are to be used prophylactically in this protocol. Clinicians caring for patients on this protocol are permitted to use these growth factors to provide optimal care for patients with severe neutropenia in accordance with the ASCO guidelines, (JCO, 12, 1994: pp2471-2508). If these growth factors are used in the acute setting of neutropenia and infection (documented or suspected), they will not be utilized prophylactically in subsequent cycles and they will not subsequently be used in lieu of dose reduction of (study agent).

#### **5.5 Toxicity Criteria**

All toxicities will be described and graded according to the NCI Common Terminology Criteria for Adverse Events (CTCAE) version 4.0. All appropriate treatment areas should have access to a copy of the CTCAE version 4.0. A copy of the CTCAE version 4.0 can be downloaded from the CTEP web site (<http://ctep.cancer.gov>). See also Section [9.2.2](#), Recording of Adverse Events.

## 6.0 PHARMACEUTICAL INFORMATION

### 6.1 TRC102

**Chemical Name:** Methoxyamine hydrochloride

**Other Names:** Methoxyamine HCl

**Classification:** Biochemical inhibitor of the BER pathway

**Molecular Formula:** CH3ONH2•HCl      **M.W.:** 83.52 Daltons

**Approximate Solubility:** At ambient temperature, TRC102 is freely soluble in water, sparingly in ethanol (70mg/mL), and slightly in DMSO (140mg/mL).

**Mode of Action:** TRC102 has the ability to interrupt the process of base excision repair (BER) by binding to apurinic/apyrimidinic sites produced during the initial step of the BER pathway. These sites are substrates for topoisomerase II (topo II); an enzyme that cleaves damaged DNA. TRC102 has demonstrated the ability to potentiate the activity of the alkylating agents temozolomide and carmustine, and antimetabolite agents fludarabine and pemetrexed, in murine models of human cancer. Therefore, TRC102 may be able to potentiate the activity of alkylating and antimetabolite chemotherapy in patients.

**Description:** TRC102, a white, crystalline solid, is the hydrochloride salt of methoxyamine.

**How Supplied:** TRC102 is supplied by IriSys, Inc. and distributed by the Pharmaceutical Management Branch, CTEP/DCTD/NCI. The white, opaque, size 2, hard gelatin capsules contain 25 mg of Methoxyamine HCl powder, microcrystalline cellulose, crosspovidone, sodium starch glycolate, colloidal silicon dioxide, and talc. Each HDPE bottle with child-resistant screw cap contains 30 capsules.

**Storage:** Store bottles of TRC102 at refrigerated temperature (2-8°C).

**Stability:** Shelf life surveillance of the intact bottles is ongoing.

**Route of Administration:** Oral

**Method of Administration:** Capsules are taken in the morning after patients have fasted for at least two hours. Take with 8 ounces of water. Capsules should be swallowed whole, do not chew or crush. Patients should refrain from eating or drinking for one hour following TRC102 dosing.

**Availability**

TRC102 is an investigational agent supplied to investigators by the Division of Cancer Treatment and Diagnosis (DCTD), NCI.

TRC102 is provided to the NCI under a Collaborative Agreement between the pharmaceutical collaborator and the DCTD, NCI (see Section [14.0](#)).

### **6.1.1 Agent Ordering and Agent Accountability**

TRC102 may be requested by the Principal Investigator (or their authorized designees) at each participating institution. Pharmaceutical Management Branch (PMB) policy requires that the agent be shipped directly to the institution where the patient is to be treated. PMB does not permit the transfer of agents between institutions (unless prior approval from PMB is obtained). The CTEP-assigned protocol number must be used for ordering all CTEP-supplied investigational agents. The responsible investigator at each participating institution must be registered with CTEP, DCTD through an annual submission of FDA Form 1572 (Statement of Investigator), Curriculum Vitae, Supplemental Investigator Data Form (IDF), and Financial Disclosure Form (FDF). If there are several participating investigators at one institution, CTEP-supplied investigational agents for the study should be ordered under the name of one lead investigator at that institution.

Active CTEP-registered investigators and investigator-designated shipping designees and ordering designees can submit agent requests through the PMB Online Agent Order Processing (OAOP) application (<https://eapps-ctep.nci.nih.gov/OAOP/pages/login.jspx>). Access to OAOP requires the establishment of a CTEP Identity and Access Management (IAM) account (<https://eapps-ctep.nci.nih.gov/iam/>) and the maintenance of an “active” account status and a “current” password. For questions about drug orders, transfers, returns, or accountability, call [contact] Monday through Friday between 8:30 am and 4:30 pm (ET) or email [[contact]](mailto:[contact]) anytime.

### **6.1.2 Agent Inventory Records**

Agent Inventory Records – The investigator, or a responsible party designated by the investigator, must maintain a careful record of the inventory and disposition of all agents received from DCTD using the NCI Oral Drug Accountability Record Form (Oral DARF). (See the NCI Investigator’s Handbook for Procedures for Drug Accountability and Storage.)

## **6.2 Temozolomide**

**Generic name:** Temozolomide

**Commercial name:** Temodar®

**Chemical name:** 3,4-dihydro-3-methyl-4-oxoimidazo[5,1-d]-*as*-tetrazine-8 carboxamide

Classification	Antineoplastic agent, alkylating
Molecular Formula:	C 6 H 6 N 6 O 2
Molecular Weight:	194.15
Mechanism of Action:	Temozolomide is not directly active but undergoes rapid non-enzymatic conversion at physiologic pH to the reactive compound 5-(3-methyltriazen-1-yl)-imidazole-4-carboxamide (MTIC). The cytotoxicity of MTIC is thought to be primarily due to alkylation of DNA. Alkylation (methylation) occurs mainly at the O  and N  positions of guanine.
Appearance:	White to light tan/light pink powder
Melting point:	Decomposes at 206°C
How Supplied:	Commercially available
Stability:	The molecule is stable at acidic pH (<5), and labile at pH >7, hence TEMODAR can be administered orally. The prodrug, temozolomide, is rapidly hydrolyzed to the active 5-(3-methyltriazen-1-yl)imidazole-4-carboxamide (MTIC) at neutral and alkaline pH values, with hydrolysis taking place even faster at alkaline pH. The product label recommends Storage at 25°C (77°F); excursions permitted to 15°-30°C (59°-86°F).
Half life:	Temozolomide is rapidly eliminated with a mean elimination half-life of 1.8 hours

### Packaging, Dispensing and Storage

TEMODAR Capsules are available in 5-mg, 20-mg, 100-mg, 140-mg, 180-mg, and 250-mg strengths. The capsules contain a white capsule body with a color cap and the colors vary based on the dosage strength. The 5-mg, 20-mg, 100-mg, 140-mg, and 180-mg capsule strengths are available in 5-count and 14-count packages. The 250-mg capsule strength is available in a 5-count package. The product label recommends Storage at 25°C (77°F); excursions permitted to 15°-30°C (59°-86°F). Labeling of the packages containing the capsules will be done in accordance with the local procedures (as required by law). According to the dosing the hospital pharmacist delivers the temozolomide dosage for a complete cycle to the subject.

## **7.0 PROCEDURES FOR PATIENT ENTRY ON STUDY**

This study is supported by the NCI Cancer Trials Support Unit (CTSU) Regulatory Office and uses the Oncology Patient Enrollment Network (OPEN).

### **Site Registration Requirements – IRB Approval**

Each investigator or group of investigators at a clinical site must obtain IRB approval for this protocol and submit IRB approval and supporting documentation to the CTSU Regulatory Office before they can enroll patients. Study centers can check the status of their registration packets by querying the Regulatory Support System (RSS) site registration status page of the CTSU member web site by entering credentials at <https://www.ctsu.org> and clicking on the RSS tab.

Site registration documents and a CTSU Transmittal Sheet (on CTSU website) must be submitted to the CTSU Regulatory Office at the following address:

CTSU Regulatory Office  
Coalition of National Cancer Cooperative Groups  
[name]  
[name]  
Phone – [name]  
Fax – [contact]  
[[contact]](mailto:[contact]) (for submission of regulatory materials only)

### **Patient Registration:**

Patient enrollment will be facilitated using the Oncology Patient Enrollment Network (OPEN). All site staff will use OPEN. OPEN is a web-based registration system available to users 9 a.m. to 4:30 p.m. Eastern Time. The system can be accessed by entering credentials at <https://www.ctsu.org> and clicking on the OPEN tab, or by entering credentials at the OPEN portal URL <https://open.ctsu.org>.

Prior to discussing protocol entry with the patient, site staff must check the ABTC website ([abtconsortium.org](http://abtconsortium.org)) for protocol status and slot availability.

Prior to accessing OPEN, site staff should verify the following:

- All eligibility criteria have been met within the protocol stated timeframes. Site staff should use the registration forms provided on the group web site as a tool to verify eligibility.
- All patients have signed an appropriate consent form and HIPAA authorization form (if applicable).

Access requirements for OPEN:

- Site staff will need to be registered with CTEP and have a valid and active CTEP-IAM account. This is the same account (user id and password) used for credentialing in the CTSU members' web site.
- To perform registrations, the site user must have been assigned the 'Registrar' role (or equivalent) on the relevant Group or CTSU roster.

The OPEN system will provide the site with a printable confirmation of registration and treatment information. Upon completion of the registration process in OPEN, sites should contact the ABTC Central Office to confirm the patient's registration.

Further instructional information is provided on the CTSU members' web site OPEN tab or within the OPEN URL (<https://open.ctsu.org>). For any additional questions contact the CTSU Help Desk at [name] or [[contact]](mailto:[contact]).

